#### *2.6.3. Measure of participation*

##### *2.6.3.1. Stroke Impact Scale (SIS)*

The 59-item Stroke Impact Scale (SIS) is a self-reported measure of health status (Appendix X). It is designed to measure various domains of stroke outcomes, including activities of daily living/instrumental activities of daily living (ADL/IADL), strength, mobility, hand function, memory and thinking, communication, emotion, and participation. Each item was rated on a 5-point scale, yielding a possible score range

from 0 to 100. Lower scores were indicative of increasing difficulty experienced by the participants in accomplishing the tasks described in the test. The MCID of the strength, ADL/IADL, mobility and hand function domains was 9.2, 5.9, 4.5 and 17.8 respectively (Lin et al., 2010).

## 2.7 Procedures for reporting and monitoring adverse events

During the treatment procedures, one case physiotherapist was responsible for the participant, monitoring changes, rectifying the intervention, recording any change of condition, and reporting any adverse events. According to the Hospital Authority regulations and guideline, the physiotherapist reported adverse events to the supervisor who reported it through the Accident or Incident Reporting System within 48 hours.

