#### 2.4.2 Experimental group

The participants in the experimental group underwent transcranial magnetic stimulation over hotspot at contralesional M1 region on weekdays over a 2-week period (i.e., 10 sessions), using a Magstim Rapid Stimulator (Magstim Company, Whitland, UK). We used a figure-of-eight coil (each loop 70 mm in diameter) for delivering the stimulation. The stimulation protocol of rTMS used was at a low frequency of 1 Hz with a stimulus intensity of 90% of rMT for a total of 1200 pulses in each session. This low-frequency protocol was adopted because the stimulation parameters were shown to result in down-regulation of motor cortical excitability over the contralesional cortex (Boggio et al., 2006). For frequencies from 0.2 to 1 Hz (low frequency), which favor the manifestation of the long-lasting inhibitory phase, may lead to cortical inhibition. Conversely, frequencies >2 Hz can mask the inhibitory phase of the preceding pulse,

thereby maintaining the neurons in a state of excitation (Moliadze et al. 2003). A meta-analysis by Zhang et al. (2017) found that low frequency rTMS was more beneficial than high frequency rTMS, and that rTMS administered to the contralesional hemisphere elicited better improvements in upper limb motor recovery than when applied to the lesioned hemisphere (Zhang et al., 2017).

The participants in the experimental group also underwent structured upper limb exercise training conducted by a registered physiotherapist in Queen Elizabeth Hospital. Each participant exercised at his or her own pace and was encouraged to perform the exercise continuously for thirty minutes in each session. In the treatment sessions during the first 2 weeks, the participants performed the 30-minute exercise training immediately after the brain stimulation. For the subsequent 10 weeks, the participants continued to receive exercise training twice per week. In each exercise session, two modes of exercises with 15 minutes for each were offered to improve task performance and dexterity of the paretic upper limb. The specific exercises included: 1. reach and grasp exercises: stacking cones or placing cones, and 2. fine motor control exercises of the hand .

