#### 2.4.3 Sham group

The sham group received sham rTMS with a trained physiotherapist. All procedures were exactly the same (identifying the hotspot, etc.), except that sham rTMS was given. Sham stimulation was conducted by positioning the coil at an angle of 90 degrees relative to the scalp instead of tangentially to the hotspot, but the coil produced the same sounds as in real rTMS. This strategy allowed the magnitude of the field delivered to be decreased but did not eliminate it (Lisanby et al., 2001) and created a similar sensation. The participants in the sham control group underwent the same upper limb exercise program as those in the experimental group.

[figure not shown]

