## 2.5. Outcome assessment

### 2.5.1 Blinded assessors

Two independent physiotherapists with more than 3 years of relevant experience in neurological rehabilitation were responsible for conducting the evaluations at different time points. These assessors were blinded to group allocation. Evaluations were performed at 3 different time points (figure 6): baseline measurement (Time 0), post-brain stimulation (Time 1), and 12-week follow-up (Time 2) (Figure 6).

A meeting and workshop conducted by the chief investigator were conducted to familiarize the two assessors with the assessment tools and procedures before the trial officially commenced. Regular discussions were conducted at three-month intervals for quality assurance purpose.

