#### *2.6.1.2 Motor evoked potential (MEP)*

To obtain the MEP of the FDI, EMG activity was measured using silver–silver chloride (Ag-AgCl) electrodes placed on the skin overlying the FDI. The peak-to-peak MEP amplitude was recorded, which reflects cortical excitability (Malcolm et al., 2007) (Figure 7). Ten averaged MEPs evoked from the M1 hotspot on both the ipsilesional and contralateral sides at 120% rMT were recorded using the Magstim 200 (Magstim Company, Whitland, UK). If the EMG could not be triggered at 100% of the resting motor threshold, the MEP was defined as “cannot be triggered” and set at zero.

If the MEP was absent when stimulating the lesioned hemisphere by the stroke, the motor hotspot was defined as being symmetrical to the contra-lesional hemisphere. The signal was amplified, bandpass filtered (1-5k Hz), and digitized for off-line analysis with ADC sampling rate of 3kHz by a built-in EMG device in Brainsight 2 (Brainsight 2, Rogue Research Inc., Montreal, Canada).

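### Adverse-event recording is tied to treatment sessions, with no fixed enquiry, no cover for assessment TMS and no summary by arm

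*Combined protocol and SAP*

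**What the plan says.** - **Who records, and when.** Section 2.7: "During the treatment procedures, one case physiotherapist was responsible for the participant, monitoring changes, rectifying the intervention". The same sentence adds "recording any change of condition, and reporting any adverse events". It gives no event list, no set question, no start or end date, and no mention of the assessment visits.
- **Where reports go.** Section 2.7: "the physiotherapist reported adverse events to the supervisor who reported it through the Accident or Incident Reporting System within 48 hours". No trial dataset is named.
- **TMS outside treatment.** Section 2.6.1.2: "Ten averaged MEPs evoked from the M1 hotspot on both the ipsilesional and contralateral sides at 120% rMT were recorded". Section 2.8 analyses MEP over three time points, so this testing takes place at Times 0, 1 and 2. Section 2.4.1 also has the hotspots in both hemispheres located at the initial assessment session.
- **Who is blinded.** Section 2.1 names assessors and patients. Section 2.5.1 says of the two outcome assessors: "These assessors were blinded to group allocation". They have no stated adverse-event task.
- **Analysis.** Section 2.8 does not mention adverse events.

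**The concern.** A trial of repeated brain stimulation will be read for tolerability as well as efficacy, whether or not safety is a formal objective. The recording rule is tied to time under treatment and depends on what the physiotherapist notices or is told. A participant who has a headache at home, or shoulder pain after training, need not be asked about it. An event that follows MEP testing at an assessment has no recording procedure of its own. If the trial then reports no adverse events, the reader cannot tell whether few occurred or few were sought. Events that were never asked about cannot be recovered reliably afterwards. With no planned table by arm, even the events that are recorded may stay in the hospital incident system and never reach the trial report.

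**Working it through.** The plan gives no safety figure to reproduce, so the main check sets the contact schedule against the recording rule.

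**1. Contact under treatment (sections 2.4 and 2.4.2).** There are 10 stimulation sessions in weeks 1–2, then 2 per week × 10 weeks = 20 exercise sessions. The total is 10 + 20 = 30 session days in 12 × 7 = 84: 10 of 14 in weeks 1–2 and 20 of 70 in weeks 3–12. Contact therefore continues to week 12, but 84 − 30 = 54 days have no session. This counts opportunities to hear of an event. It is not a capture rate.

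**2. TMS exposures against the rule.**

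| TMS given | Covered by the wording of 2.7? | Later session at which an event could be mentioned? |
|---|---|---|
| Treatment sessions, weeks 1–2 | Yes | Yes |
| Time 0 assessment | No | Yes, first treatment session |
| Time 1 assessment | No | Yes, exercise sessions in weeks 3–12 |
| Time 2 assessment | No | None described |

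**3. What incomplete capture does to a null result.** The planned total is 24 (section 2.2.2), allocated 1:1 (section 2.3), so 12 per arm. Let p be the true proportion of participants with an event and c the proportion of those who are recorded. Both are assumptions; the documents give neither.

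The chance of recording at least one affected participant in an arm is 1 − (1 − c·p)^12:

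| p | c = 1 | c = 0.5 |
|---|---|---|
| 5% | 1 − 0.95^12 = 0.46 | 1 − 0.975^12 = 0.26 |
| 10% | 1 − 0.90^12 = 0.72 | 1 − 0.95^12 = 0.46 |
| 20% | 1 − 0.80^12 = 0.93 | 1 − 0.90^12 = 0.72 |

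With zero recorded in 12, the one-sided 95% upper limit on the recorded rate c·p is 1 − 0.05^(1/12) = 0.221. Dividing by c gives the limit on p: 22% at c = 1, 0.221/0.75 = 29% at c = 0.75, and 0.221/0.5 = 44% at c = 0.5. The 22% is due to sample size alone, and better recording will not lower it. The excess over 22% is due to incomplete capture.

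**The case against.** The strongest reply is that section 2.7 is broader than it first looks. It asks for any change of condition to be recorded, without limiting this to events that start in the session, and sessions run to week 12. A headache at home can be noted at the next visit. Participants are screened for TMS safety, rTMS contraindications are excluded, and section 2.7 refers to Hospital Authority rules that are not supplied and may ask for more. The outcomes are FMA and MEP, no safety objective is stated, and 12 per arm cannot support a useful safety comparison. MEP testing is the same in both arms, so leaving it out creates no obvious bias between them.

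Most of this stands, and it keeps the point small. It does not supply a fixed question, cover Time 2, or provide a table.

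Four stronger readings are tempting and are not supported:

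- **The recorder sees the allocation.** Section 2.4.3 says "Sham stimulation was conducted by positioning the coil at an angle of 90 degrees relative to the scalp", so the operator holding the coil knows the arm. Section 2.7 does not say that the case physiotherapist is that operator or is present at stimulation. The text supports only that this person is not stated to be blinded.
- **Events at home are missed.** The plan has no set enquiry for them, but it does not exclude them.
- **Action can wait two days.** The words "reported it through the Accident or Incident Reporting System within 48 hours" apply to the supervisor's filing. They set no delay before anyone responds.
- **The arms are compared unblinded.** No comparison of events by arm is planned at all.

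**Conclusion.** The point holds and is minor. The described procedure has no fixed enquiry between sessions, no cover for assessment TMS (with no later session at all after Time 2), no recorder stated to be blinded, and no summary by arm. A report of no adverse events under this plan would be weak evidence of tolerability. On 12 per arm, the upper limit on the true rate would be 22% with complete capture and 44% if half of affected participants were recorded. The actual capture rate is unknown. The FMA and MEP conclusions are unaffected.

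The verdict assumes that the unsupplied appendices and hospital regulations contain no structured adverse-event enquiry for this trial. The one safety form described in the text (section 2.4.1) is for screening at recruitment. The documents also give no basis for ranking the risk of the assessment pulses against that of the treatment pulses. The point about assessments concerns coverage only.

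**What to change.** **Section 2.7.** Set the collection window from first TMS exposure to the end of the Time 2 visit, and state that TMS given at assessments is included. Use one fixed event checklist with a question about the time since the last visit, at the start of each session and at Times 1 and 2. At Times 1 and 2, have the blinded participant complete it, or have it asked only after all outcome tests are finished, so that answers cannot influence FMA scoring. Placing it last also takes in the MEP testing just done. Events that begin after the participant leaves Time 2 remain outside the window, and the report should say so.

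**Section 2.8.** Add a descriptive table of events by arm, with no hypothesis test.

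**Cost.** A few minutes per visit at visits that already take place, with existing staff. More minor events will be recorded in both arms. A small unblinding risk remains if assessors see the answers before scoring. Nothing here alters treatment or its management, which stay with the site.

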## 2.8. Statistical analysis

The software package SPSS 21.0 for Windows (IBM, Armonk, NY, USA) was used for statistical analysis. The demographic characteristics of the participants and outcome variables at baseline were compared using the Chi-square test (for nominal data), Mann-Whitney U test (for ordinal data), and independent t-test (for continuous

data). Next, for each continuous outcome measure (FMA, MEP, GS, ARAT, B&B, RT), a  $2 \times 3$  two-way repeated measures ANOVA (mixed design; within-subject factor: time; between-subject factor: group) was used to determine whether there was a significant treatment effect on each of the outcome variables (i.e., significant group  $\times$  time interaction effect). If any substantial difference was found in particular baseline characteristics between the two groups, the variables would be entered as covariates in the above ANOVA model. Post-hoc analysis was then performed to examine the within-group changes over time using paired t-tests and between-group differences in change score at week 2 and week 12 using independent t-tests.

For analysis of the NHPT, because the failure cases were assigned a value of 600s, non-parametric statistics was used. Friedman test and post-hoc Wilcoxon test were used to examine the within-group changes over time, while Mann-Whitney U test was used to examine the difference between the two groups at week 2 and 12.

Next, for those clinical outcome variables that yielded a significant treatment effect (i.e., significant group  $\times$  time interaction effect), Pearson's product moment correlation coefficients were used to determine the degree of correlation between changes in these variables and those in MEP on both sides.

Intention to treat analysis was first conducted. Any missing data would be substituted using the last-observation-carried-forward (LOCF) method. This was followed by on-protocol analysis, in which only those participants who completed all outcome assessments were included.

The alpha was set at 0.05, except for post-hoc tests where the alpha was adjusted to 0.025 (i.e., Bonferroni correction) because of the 2 comparisons made (within-group analysis: baseline Vs week 2; week 2 Vs week 12; between-group comparison of change score: week 2 and week 12).

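### Section 2.8 makes baseline adjustment depend on an undefined trigger and leaves the week-2 and week-12 group comparisons without it; each outcome's own baseline should be a covariate fixed in advance

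*Combined protocol and SAP*

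**What the plan says.** Section 2.8 begins with baseline comparisons: "The demographic characteristics of the participants and outcome variables at baseline were compared using the Chi-square test", with other tests for ordinal and continuous data. For FMA, MEP, grip strength, ARAT, Box and Block and reaction time, the treatment effect is the group × time interaction in a 2 × 3 mixed ANOVA, in which baseline is one of the three time levels.

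The adjustment rule is "If any substantial difference was found in particular baseline characteristics between the two groups, the variables would be entered as covariates". No p-value, standardised difference or clinical margin says what is substantial, and no variable is listed. The rule has one destination: "the variables would be entered as covariates in the above ANOVA model".

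The follow-up comparisons are "between-group differences in change score at week 2 and week 12 using independent t-tests", at alpha 0.025, with no covariate mentioned. For NHPT, "Mann-Whitney U test was used to examine the difference between the two groups at week 2 and 12", with no baseline term stated. The interaction result also selects what is correlated with MEP change: "for those clinical outcome variables that yielded a significant treatment effect".

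Section 2.6 makes FMA and MEP the primary outcomes, and both go through this model. Section 2.2.2 asks for 24 patients. Section 2.3 describes blocked 1:1 allocation and mentions no stratification.

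**The concern.** In a trial this small, chance baseline differences of half a standard deviation are common. The plan's response is left to judgement once the baseline data are seen: whether a difference is large enough, and which variables count. A reader cannot tell from Section 2.8 which model will produce the primary result.

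If the rule does operate, it changes the interaction test but not the t-tests that give the size of the effect at each week, so the two come from different models. A change score is not a full substitute for adjustment. It subtracts the whole baseline gap, whereas only a fraction r of that gap is expected to persist. The reported difference is therefore pushed against whichever group started better. At stake are the sign and size of chance errors in the reported FMA and MEP differences, and a fixed choice of primary model.

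**Working it through.** **Inputs from the documents.** 24 patients (Section 2.2.2) at 1:1 (Section 2.3), so 24/2 = 12 per arm; alpha 0.05 for the interaction and 0.025 for post-hoc tests (Section 2.8); FMA MCID 5.2 points (Section 2.6.1.1). The plan gives no figure of its own on baseline adjustment to reproduce.

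**Assumptions.** Normal data, equal SDs, and the same correlation r between any two visits, shown at 0.5, 0.7, 0.8 and 0.9. Where power or estimates are shown, the true difference is 0.6 SD at both follow-up visits. Section 2.2.2 gives an effect size of about 0.6 without saying on what scale, so 0.6 SD is illustrative.

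**1. Chance imbalance.** The SE of a baseline mean difference is √(2/12) = 0.408 SD. P(|gap| > 0.5 SD) = 2(1 − Φ(0.5/0.408)) = 22%, or 11% each way.

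**2. Bias of the change score.** Given a baseline gap, the expected follow-up difference is effect + r × gap. Subtracting the gap leaves effect − (1−r) × gap. For a 0.5 SD gap the shift is 0.25, 0.15, 0.10 and 0.05 SD. ANCOVA removes r × gap and leaves about zero. On the FMA, a 10-point gap (chosen for illustration) shifts the difference by 5, 3, 2 or 1 points, against the MCID of 5.2. The chance of such a gap is 1, 10 or 22% for an assumed SD of 10, 15 or 20.

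**3. Interaction test with no covariate entered, own-baseline gap above 0.5 SD.** These are simulated powers. The planned test is the univariate F on 2 and 44 df; the adjusted test is the joint test of group at both weeks, F on 2 and 20 df.

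| r | Unadjusted, experimental starts better | Unadjusted, experimental starts worse | Own-baseline adjusted, either way |
|---|---|---|---|
| 0.5 | 6% | 65% | 35% |
| 0.7 | 20% | 74% | 46% |
| 0.8 | 41% | 84% | 60% |
| 0.9 | 84% | 97% | 87% |

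A p<0.05 trigger on own baseline fires in 5% of trials, so it can reach at most 5 of the 22 percentage points. It fires in only about 0.5% of trials with a gap near 0.5 SD.

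**4. When the rule fires on own baseline (p<0.05, mean gap 0.91 SD).** The unadjusted week-12 difference averages 0.6 − (1−r) × 0.91 if the experimental group started better and 0.6 + (1−r) × 0.91 if it started worse. At r = 0.5 that is 0.6 ∓ 0.455 = 0.145 or 1.055; at r = 0.9 it is 0.6 ∓ 0.091 = 0.509 or 0.691. Simulation over the four r values gives 0.14–0.51 SD and 0.69–1.06 SD. ANCOVA gives 0.59–0.62 SD.

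**5. Overall level.** With the trigger read as own-baseline p<0.05, the interaction type I error over all randomisations is 4.4–4.8%. The adjusted joint test has 4.9–5.1%.

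**6. Efficiency.** The large-sample variance ratio of ANCOVA to change score is (1+r)/2 = 0.75, 0.85, 0.90, 0.95. Estimating the slope with 12 per arm multiplies this by about 1 + 1/20 = 1.05, giving 0.79, 0.89, 0.95 and 1.00. Omnibus power, planned against adjusted joint test, is 29 vs 37–38, 46 vs 50, 63 vs 64 and 92 vs 90%.

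**The case against.** The strongest reply is that the plan's tests are valid, that change scores already use baseline, and that the rule deals with large imbalances. Validity over all randomisations stands (step 5). The second point stands in part: baseline is subtracted, but the remainder in step 2 is not removed. The third fails for the t-tests, which the rule never reaches, and for moderate gaps, where a significance trigger would rarely fire.

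Several stronger readings are tempting, and the documents do not support them:

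- *The plan inflates type I error.* Interaction error of 16, 11, 9 and 7% arises at r = 0.5, 0.7, 0.8 and 0.9 only if the outcome's own baseline lies outside the rule, and then only within the 5% of trials where that baseline differs at p<0.05. Section 2.8 compares outcome variables at baseline shortly before stating the rule, so the natural reading includes them, although the text does not say so. An error of 6.2–7.1% would need the analyst to report whichever interaction is significant, which nothing in the plan permits.
- *The t-tests will often contradict the adjusted interaction.* A significant adjusted interaction with no significant between-group t-test is mainly a problem when the experimental group started significantly better. With a true 0.6 SD effect it occurs in 0.2–0.6% of all trials.
- *Own-baseline adjustment removes the effect of chance imbalance.* It does so only for that outcome's baseline. Imbalance in other factors, such as time since stroke (between 1 and 6 months in Table 1), remains.
- *The lack of stratification is a fault.* It explains why imbalance is possible, but it is not an analysis error.

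For NHPT, the alpha paragraph's "between-group comparison of change score: week 2 and week 12" suggests that changes are compared, but the NHPT sentence does not settle it. NHPT is secondary in any case.

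It can also be said that two sentences would cure the defect: name the covariates, and use them in the contrasts. That is the core of it. But own baseline is already a time level in the planned ANOVA, so entering it as a covariate uses it twice, and a matching omnibus test should be stated.

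**Conclusion.** The point holds as a modest, correctable weakness in the primary analysis. Section 2.8 leaves the model open and reports week-2 and week-12 differences with a bias of (1−r) times any chance baseline gap. Adjustment also gains some efficiency at r of about 0.5 to 0.7. It should not be read as a finding of overall type I error inflation or of frequent contradictory results.

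The sizes rest on 12 per arm, normal data with equal SDs and equal correlations, an assumed 0.6 SD effect, and an r that the documents do not give. At r near 0.9 the bias is small and the power gain disappears; the remaining benefit is a model fixed in advance. For MEP, with an assumed 20–40% of values set at zero, there is almost no power gain, so the case there is again the fixed model.

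**What to change.** Delete the conditional rule. For each continuous outcome:

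1. Model the week-2 and week-12 values with group, visit, group × visit, the outcome's own baseline and baseline × visit, with unstructured covariance.
2. Test the treatment effect with the joint 2-df test of group at weeks 2 and 12, and use the same test to select outcomes for the MEP correlations. With 24 patients complete or filled by LOCF, this is the Wilks test, exact F on 2 and 20 df. An uncorrected Wald F on 2 and 21 df from the mixed model errs 5.7–5.8%.
3. Report the adjusted group difference with its confidence interval at each visit, alpha 0.025, in place of the change-score t-tests.
4. Name any other prognostic covariate in advance.

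For NHPT, state what is compared; rank-ANCOVA on baseline ranks at each visit is a consistent option.

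The cost is SAP wording and about one degree of freedom per visit, with no new data. At r of about 0.9 or more there is no gain or a slight loss (92 vs 90% power). If the effect is present at one visit only and r is 0.8–0.9, the joint test has about 4 points less power than the planned ANOVA.

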#### 2.2.2. Sample size estimation

The sample size was estimated from previously published data on one of the primary outcome measures, the motor-evoked potential (MEP). In a study involving a sample of 20 people by Takeuchi et al. (Takeuchi et al. 2008), a significant improvement in MEP was shown in the intervention group. The estimated effect size was about 0.6. Based on this, with the power set at 90% and  $p < 0.05$ , the minimum estimated sample size would be 22. When considering a 10% attrition rate, the minimum sample size required would be 24 individuals with stroke.

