## 2.3 Randomization and allocation concealment

The recruited individuals were randomly assigned to either the experimental group or the sham group by drawing a pre-set sealed opaque envelope. The group allocation was determined by the results of a randomized table set with  $4 \times 6$  blocks with an allocation ratio of 1:1. The results were printed and placed in separate envelopes. The envelopes were then numbered and put in sequence. Once the individual was recruited, he or she was assigned the next envelope in the sequence. The randomization was done by a researcher who was not involved in the outcome assessments.

The details of the clinical trial were explained to the potential participants by the investigators, and written informed consent was obtained before the commencement of data collection (Appendix I, II, III and IV). This trial protocol was approved by the Research Ethics Committee (Kowloon Central/Kowloon East) of the Hospital Authority (Appendix V), and the Human Research Ethics Subcommittee of the Hong Kong Polytechnic University (Appendix VI).

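### As most naturally read, the only rTMS-versus-sham test of the Nine-Hole Peg Test (NHPT) ignores its baseline, and on no reading is baseline a covariate; a rank ANCOVA would be a cheap, modest improvement

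*Combined protocol and SAP*

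**What the plan says.** All references are to the combined protocol and SAP.

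- **The NHPT test.** Section 2.8 takes the NHPT out of the mixed ANOVA because failures are entered as 600 s. Friedman and Wilcoxon tests cover change within each group. For the treatment comparison, "Mann-Whitney U test was used to examine the difference between the two groups at week 2 and 12". No baseline term is named.
- **The other outcomes.** The ANOVA applies "for each continuous outcome measure (FMA, MEP, GS, ARAT, B&B, RT"), a list without the NHPT. Its post-hoc step compares "between-group differences in change score at week 2 and week 12 using independent t-tests".
- **Covariates.** If baseline characteristics differ substantially, "the variables would be entered as covariates in the above ANOVA model".
- **Alpha.** The closing sentence sets 0.025 for post-hoc tests and describes them as including "between-group comparison of change score: week 2 and week 12", without naming or excluding the NHPT.
- **Baseline data.** Section 2.5.1 schedules "baseline measurement (Time 0), post-brain stimulation (Time 1), and 12-week follow-up (Time 2"), so a baseline NHPT exists.
- **Allocation.** Section 2.3 describes "blocks with an allocation ratio of 1:1" and names no stratification factor.

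**The concern.** The change-score wording used for the ANOVA outcomes is absent from the NHPT sentence, so follow-up times are the natural reading. The covariate rule cannot fill the gap: it belongs to a model that excludes the NHPT, and it acts only after an imbalance has been seen. The Friedman and Wilcoxon tests use baseline but do not compare rTMS with sham. The baseline comparison of the groups is not a treatment comparison. Last observation carried forward may put a baseline value into a dropout's follow-up, but that is imputation and not adjustment.

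With about 12 patients per arm and no stratification on dexterity, the arms can start apart by chance. An unadjusted follow-up test carries that difference into the trial's only treatment comparison on the NHPT. It also gives up whatever precision the baseline offers. The FMA and MEP analyses are not affected.

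**Working it through.** **The plan's own figure.** There is no power or sample-size figure for the NHPT. Section 2.2.2 gives 22 patients, or 24 with 10% attrition, for MEP at 90% power ("The estimated effect size was about 0.6"). The 22 is reproduced if 0.6 is Cohen's f for the between-group factor of a repeated-measures ANOVA with 3 visits and an assumed within-patient correlation of 0.5. The noncentrality is f²·N·m/(1+(m−1)ρ) = 0.36 × 22 × 3/2 = 11.88, giving power 0.906; N = 20 gives 0.874. For attrition, 22/0.9 = 24.4, close to the stated 24. At 1:1 this is 12 per arm. The point below uses only the 12 per arm.

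**Inputs not in the documents (assumed).**
- NHPT effect: 0.6 SD, borrowed from the MEP figure, and 1.2 SD (for two equal groups d = 2f = 1.2 if 0.6 is f).
- Failures at 600 s: about 9%, varied from 0 to 40%.
- Correlation of baseline with follow-up: 0 to 0.85. Section 2.6.2.2 gives an ICC of 0.85, but that is test-retest reliability and only an upper guide for patients still recovering.
- Two-sided alpha 0.025 per visit. In the NHPT paragraph only the Wilcoxon test is called post-hoc, so this too is an assumption.

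**Model.** Baseline and follow-up log times are bivariate normal. The rTMS follow-up is shifted down by the effect, and times are capped at 600 s and tied at the worst rank. There were 40,000 simulated trials per cell, and 200,000 for conditional error rates.

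**Large-sample guide.** Relative to an unadjusted comparison, the variance factor is 1 − r² for ANCOVA and 2(1 − r) for change. At r = 0.3, 0.5 and 0.7 these are 0.91, 0.75 and 0.51 against 1.4, 1.0 and 0.6.

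**Power, 9% failures.**

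| Correlation | 0 | 0.3 | 0.5 | 0.7 | 0.85 |
|---|---|---|---|---|---|
| Rank ANCOVA, 0.6 SD | 0.18 | 0.20 | 0.23 | 0.32 | 0.52 |
| Mann-Whitney on log-time change, 0.6 SD | – | 0.14 | 0.18 | 0.31 | 0.57 |
| Mann-Whitney on change in seconds, 0.6 SD | – | 0.10–0.12 | 0.13–0.16 | 0.21–0.26 | 0.40–0.49 |
| Rank ANCOVA, 1.2 SD | 0.66 | 0.70 | 0.78 | 0.90 | 0.99 |

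Mann-Whitney on follow-up times has 0.17–0.18 at 0.6 SD and 0.65–0.67 at 1.2 SD, whatever the correlation. The ranges for seconds are for log SD 1.0 to 0.5. With 40% failures, rank ANCOVA at 0.6 SD has 0.19, 0.21, 0.28 and 0.43 at correlations 0.3 to 0.85, against 0.16–0.17 unadjusted. At alpha 0.05 with 9% failures it has 0.27, 0.29, 0.33, 0.43 and 0.64 at correlations 0 to 0.85, against 0.26–0.28.

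**Cost when baseline is uninformative.** Over all randomisations the error rate is about 2.4% for Mann-Whitney and 2.4–2.7% for rank ANCOVA, so the table slightly flatters the latter. With critical values matched on actual error (effects of 1.0 and 1.3 SD; 0, 25 and 50% failures), rank ANCOVA loses 1.4–2.4 points at correlation 0 and 0.2–1.2 at 0.2. It gains 0.8–2.0 at 0.3, 7–9 at 0.5 and 17–25 at 0.7.

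**Chance imbalance.** The SD of the baseline difference is √(2/12) = 0.41, so 22% of randomisations start more than 0.5 SD apart. In these, with no treatment effect, Mann-Whitney on follow-up times rejects in 3.6%, 5.2%, 7.9% and 9.5% at correlations 0.3, 0.5, 0.7 and 0.85; rank ANCOVA rejects in 2.7–2.9%. A baseline Mann-Whitney test at 0.05 flags only about 23% of them, so adjusting only after a detected imbalance would miss most.

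**Effect estimate.** With rank 1 fastest and rTMS coded 1, the difference in mean ranks is N × (P(rTMS slower) − 0.5). So P(rTMS faster) = 0.5 − coefficient/N. The ordinary regression interval for this is unsuitable: at 0.6 SD its upper limit passes 1 in about 33%, 29%, 20%, 9% and 2% of trials at correlations 0 to 0.85, and at 1.2 SD in 81% falling to 29%.

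**The case against.** The strongest reply is that nothing is broken. Mann-Whitney on follow-up times holds its error rate over all randomisations, and the NHPT is one of several secondary measures. That stands. A reader might infer from the conditional error rates that the planned test is biased or invalid; the documents do not support this, because those rates describe only the randomisations that happen to start apart.

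A reader might also infer that the plan certainly discards baseline. The closing alpha sentence speaks of change scores at the same two visits, so a change-score test may have been meant. The case for rank ANCOVA is then weaker: it gains at correlations 0.3–0.5, is level with log-time change at 0.7 and is slightly lower at 0.85 (0.52 against 0.57). It is mostly better than change in seconds, the recorded scale. The exception found is at correlation 0.85 and log SD 0.5 with 25–40% failures, where seconds are level or marginally ahead (0.49 against 0.49; 0.44 against 0.43). Change scores also record failure at both visits as 600 − 600 = 0, that is, no change.

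Finally, it is tempting to take the ICC of 0.85 as the correlation and claim power of 0.52. Section 2.6.2.2 gives it as test-retest reliability. Patients enter 1 to 6 months after stroke and are followed to week 12, so the correlation may be well below it. At 0.5 or less, power for a 0.6 SD effect is poor with either test.

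**Conclusion.** The point holds as a low-severity improvement for a secondary outcome. Baseline NHPT is collected but is a covariate on no reading of section 2.8, and on the most natural reading the treatment comparison does not use it at all. Against that reading, adjustment adds about 2 points of power at correlation 0.3, 5 at 0.5, 14 at 0.7 and 34 at 0.85 (from about 0.18, at 0.6 SD). The downside is about 1 to 2 points if the correlation is near 0 to 0.2. These sizes rest on an assumed effect, failure share, correlation and alpha for this test. That baseline is not a covariate rests on the text alone.

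**What to change.** For the NHPT at week 2 and at week 12, regress the rank of the follow-up time on group and the rank of baseline NHPT, with 600 s as the tied worst rank and 0.025 per visit. Adjust in every case, not only after an observed imbalance. A permutation p-value is preferable because only about 24 patients are analysed. This wording also settles whether follow-up times or change scores are meant.

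Report group medians and the number of 600 s values per group. If the baseline-adjusted probability that an rTMS patient is faster is reported, give it an interval that stays within 0 to 1, for example on the logit scale or by bootstrap. Keep Friedman and Wilcoxon as within-group description.

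The cost is analysis wording and the small power loss named above; no new data are needed. Section 2.8 is written in the past tense, so the analysis may already have been run. In that case report the rank ANCOVA beside the original test and label it as added later.
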